4. STUDY DESIGN

4.1. Overall Design

This is a multi-centre, randomized, double blind, double-dummy, 3-arm parallel group study. Eligible subjects will be randomized in a ratio of 1:1:1 to UMEC/VI inhalation powder (62.5/25 mcg once daily) administered via the ELLIPTA™ dry powder inhaler, or UMEC (62.5 mcg once daily) administered via the ELLIPTA™ or salmeterol (50 mcg BID) administered via the DISKUS.

There will be a total of 5 clinic visits and one follow-up phone call (Visit 6). A pre-screening visit (Visit 0) may be required in order to administer the informed consent before any changes are made to the subject's current medication regimen. If no changes in medication are required, V0 (pre-screening) and V1 (screening) may be conducted on the same day. Inhaled long-acting muscarinic antagonist (LAMA) or long-acting beta₂-agonist (LABA) and/or albuterol/salbutamol as needed (rescue medication) are not exclusionary prior to Screening or during the run-in.

Eligible subjects at Screening Visit 1 will be current or former smokers, at least 6 weeks ICS and ICS/LABA free with an FEV₁ post-albuterol/salbutamol of $\geq 30\%$ to $\leq 80\%$ predicted normal and a FEV₁/FVC < 0.7 and a CAT score ≥ 10 .

Subjects using inhaled LAMA or LABA medication must withhold their morning dose prior to Screening spirometry. Subjects who meet all other eligibility criteria at Screening will enter a run-in period for 4 weeks. During the run-in period, subjects will continue with their inhaled LAMA or LABA medication. In addition, subjects will be provided with short acting albuterol/salbutamol as needed for relief of COPD symptoms (rescue medication) throughout the study.

Subjects who experience a moderate or severe COPD exacerbation during the run-in period will be deemed run-in failures. Subjects who experience a mild COPD exacerbation, defined as worsening of symptoms that requires **no** treatment with antibiotics or steroids and is self managed by the patient by an increase of inhaled rescue medication, ([Appendix 5](#)), will be able to continue in the study based on the judgment of the investigator and agreement of the sponsor's medical monitor.

At the randomization Visit 2 (Day 1), those subjects who successfully complete the run-in period as well as meet the other pre-defined eligibility and randomization criteria will be randomized to one of the 3 treatment arms for 24 weeks.

In addition, a subset of subjects (approximately 150 per treatment arm) will undergo assessment of their physical activity measured through a physical activity monitor (Actigraph GT9X) worn for 7 days from Screening (Visit 1), for 7 days from Randomisation (Visit 2), 7 days from Visit 3, and for 7 days prior to last clinic Visit (Visit 5).

The occurrence of adverse events (AEs) will be evaluated throughout the study beginning at Visit 2 (Day 1) and until the follow-up contact (Visit 6). Serious adverse events (SAEs) will be collected over the same time period as AEs. However, any SAEs assessed as related to study participation (e.g., study treatment, protocol-mandated procedures, invasive tests, or change in existing therapy) or related to a GSK concomitant medication, will be recorded from the time a subject consents to participate in the study up to and including any follow up contact ([Appendix 4](#)).

All subjects will be given an electronic diary (eDiary) for use during the run-in, and the treatment period to complete PRO questionnaires, record COPD daily symptoms, any medical problems experienced during the study and the time they take their COPD medications. Daily rescue medication usage (number of inhalations taken in the last 24h) will also be captured in the eDiary. In addition, and in some countries, rescue medication use will also be captured by the use of electronic metered dose inhaler (eMDI).

At Screening Visit 1, all subjects must be trained on the proper use of their existing COPD medications inhalation devices and instructed to strictly adhere to and record the time they take their COPD medications in the eDiary.

At the randomization Visit 2, all subjects must be trained on the proper use of the ELLIPTA and DISKUS inhalation devices and instructed to strictly adhere to and record the time they take their study medications in the eDiary.

[figure not shown]
All subjects must be trained on the correct use of the eDiary and instructed to complete the eDiary during the run-in and treatment period.

Subjects will be considered to have completed the study upon completion of the follow-up contact by telephone.

There are no plans to routinely provide any of the study treatments for compassionate use following study completion as the study treatment are commercially available.

The study design schematic is illustrated in [Figure 1](#)

Figure 1 Study Schematic

*Subjects may continue the use of inhaled LAMAs or LABAs and/or study provided albuterol/salbutamol as needed (rescue medication) during the run-in while adhering to the withholding of other COPD medications detailed in the Exclusion Criteria.

4.2. Treatment Arms and Duration

Subjects will be stratified based on long-acting bronchodilator usage during the run-in (none or one long-acting bronchodilator per day) and randomized in a ratio of 1:1:1 to either

- UMEC/VI 62.5/25 mcg once daily via ELLIPTA + placebo twice daily via DISKUS
- UMEC 62.5 mcg once daily via ELLIPTA + placebo twice daily via DISKUS
- Salmeterol 50 mcg twice daily via DISKUS + placebo once daily via ELLIPTA

The total duration of subject participation in the study will be approximately 29 to 35 weeks consisting of 6 weeks pre-screening if necessary, 4 weeks run-in, 24 week treatment and one week follow-up.

4.3. Type and Number of Subjects

Approximately 3232 will be screened globally in approximately 240 sites such that approximately 2424 subjects will be randomized and approximately 2181 evaluable subjects complete the study.

4.4. Design Justification

A randomized, double blinded, parallel group study is a standard, well-established design to evaluate the efficacy and safety of an investigational drug. A salmeterol arm is included to allow a comparison to be made between UMEC/VI, UMEC with salmeterol, a standard practice treatment.

The double-dummy design is appropriate when drugs are of different appearance or different administration regimen which is appropriate in this study where the inhalers used have a different appearance and used once daily and twice daily.

The European Medicines Agency (EMA) COPD Guidelines suggest that duration of 12 to 24 weeks is considered adequate for assessment of response of COPD symptoms to treatment intervention with bronchodilators (EMA COPD guidelines, 2012).

The primary endpoint is trough FEV₁ at week 24. This endpoint is generally considered to be a robust, well established and an objective means to show the efficacy of a bronchodilator [Dahl, 2010; Feldman, 2010].

Other endpoints such SAC TDI, E-RS, SGRQ-C, CAT, Subject Global Rating of Change in global impression of disease severity are captured to allow responder analyses and to provide comparative data on PROs between the treatment groups.

4.5. Dose Justification

This study is intended to evaluate the efficacy of marketed doses of UMEC/VI (62.5/25mcg once daily), UMEC (62.5 mcg once daily) and salmeterol (50mcg twice daily) that are approved for the maintenance treatment of COPD, with respect to PRO measures.

4.6. Benefit: Risk Assessment

Summaries of findings from both clinical and non-clinical studies conducted with UMEC/VI and UMEC can be found in the investigator's brochures (IB) [GlaxoSmithKline Document Number [RM2009/00437/07](#)] and [GlaxoSmithKline Document Number [RM2006/00835/09](#)] and in the label information sheets. The current safety profile for UMEC (62.5mcg) and the UMEC/VI (62.5/25mcg) based on data available to date, is comparable with other LABAs and LAMAs. Summary safety data can also be found in the information sheet for salmeterol [[Serevent product information](#), 2003]. The following section outlines the risk assessment and mitigation strategy for this protocol:

4.6.1. Risk Assessment

Potential Risk of Clinical Significance	Summary of Data/Rationale for Risk	Mitigation Strategy
Investigational Product (IP) [UMEC/VI]		
Severe milk protein allergy	Anoro contains Lactose monohydrate (which contains milk protein) as an excipient.	Exclusion criteria have been set for subjects with milk protein allergy.
Cardiovascular effects such as cardiac arrhythmias e.g. supraventricular tachycardia and extrasystoles.	
Class effects associated with LABAs and LAMA containing therapy. The clinical significance of these arrhythmias is unknown. Clinical experience with UMEC/VI to date in completed studies did not show any association with major cardiovascular events.
 
Data available in the product label for UMEC/VI
	
Exclusion criteria have been set for subjects with uncontrolled or severe cardiovascular disease according to the principal investigation's (PI) opinion where the potential risk may outweigh the benefit. The PI should also determine the clinical significance of abnormal ECG findings at screening and exclude subjects who would be at undue risk by participating in the trial. Patients with the following abnormalities will be excluded from participation: atrial fibrillation with rapid ventricular rate >120bpm, sustained or nonsustained ventricular tachycardia, or second degree heart block Mobitz type II or third degree heart block (unless pacemaker or defibrillator had been inserted).

Beta agonists and risk of asthma-related death	Long-acting beta agonists such as vilanterol when used alone may increase the risk of asthma-related death. A placebo-controlled trial with another LABA (salmeterol) showed an increase in asthma-related deaths in subjects receiving salmeterol. This finding with salmeterol is considered a class effect of all LABAs, including vilanterol. Data are not available to determine whether the rate of death in patients with COPD is increased by LABA.	Subjects with a current diagnosis of asthma are excluded from participation in the study.
Paradoxical bronchospasm	As with other inhaled medicines, UMEC/VI can produce paradoxical bronchospasm which may be life threatening.	If paradoxical bronchospasm occurs following dosing with UMEC/VI, this treatment should be discontinued immediately and alternative therapy should be instituted.
Use in patients with narrow-angle glaucoma or urinary retention	No association has been found to date, in completed studies with UMEC/VI or UMEC monotherapy, on glaucoma or urinary retention. However, glaucoma or urinary retention	Exclusion criterion states that subjects with medical conditions such as narrow-angle glaucoma, prostatic hypertrophy, or bladder neck obstruction should only be

Potential Risk of Clinical Significance	Summary of Data/Rationale for Risk	Mitigation Strategy
	have been observed with other antimuscarinic agents, and could potentially be due to the pharmacology.	included if, in the opinion of the principal investigator, the benefit outweighs the risk.
Use of beta blockers	Beta-adrenergic blockers may weaken or antagonize the effect of beta ₂ -agonists such as vilanterol.	The study permitted medications and non drug therapies section states that concomitant administration with beta-blockers is only permitted if, in the Investigator's opinion, the likely benefit outweighs the potential risk.
Pregnancy	There is no experience to date of pregnancy during the use of UMEC/VI.	The study inclusion criteria ensures that female subjects of child bearing potential must have a negative pregnancy test at screening, and agree to a reliable contraceptive method, used consistently and correctly (i.e. in accordance with the approved product label and the instructions of the physician for the duration of the study). Exclusion criteria include Pregnancy : Women who are pregnant or lactating or are planning on becoming pregnant during the study.
Severe hepatic impairment	UMEC/VI has not been studied in severe hepatic impairment.	Exclusion criterion states that subjects severe hepatic impairment should only be included if, in the opinion of the study physician, the benefit outweighs the risk.
Investigational product (IP) [UMEC]		
Cardiovascular effects such as cardiac arrhythmia, e.g. atrial fibrillation and tachycardia	A potential class effect associated with anti-muscarinic therapies. Data available to date in the IB for UMEC [GlaxoSmithKline Document Number RM2006/00835/09	Screening electrocardiogram (ECG) criteria to exclude subjects potentially at risk
Narrow-angle glaucoma, urinary retention	A class effect associated with anti-muscarinic therapies. Data available in the IB for UMEC [GlaxoSmithKline Document Number RM2006/00835/09	Exclusion criterion states that subjects with medical conditions such as narrow-angle glaucoma, prostatic hypertrophy, or bladder neck obstruction should only be included if, in the opinion of the study physician, the benefit outweighs the risk.
Paradoxical bronchospasm that may be life threatening	Known effect associated with inhalation therapy	A short-acting inhaled bronchodilator (albuterol/salbutamol) will be provided for use as needed throughout the study. The investigators will be instructed to assess subject's condition to determine their eligibility to

Potential Risk of Clinical Significance	Summary of Data/Rationale for Risk	Mitigation Strategy
		continue in the study and the need for alternative therapy.
Severe hepatic impairment	UMEC has not been studied in severe hepatic impairment.	Exclusion criterion states that subjects with severe hepatic impairment should only be included if, in the opinion of the study physician, the benefit outweighs the risk.
Pregnancy/Lactation	There is no experience to date of pregnancy during the use of UMEC.	The study inclusion criteria ensure that female subjects enrolled, who are of Child bearing potential, have a negative pregnancy test at screening, and agree to a reliable contraceptive method, used consistently and correctly (i.e. in accordance with the approved product label and the instructions of the physician for the duration of the study). Exclusion criteria states - Pregnancy: Women who are pregnant or lactating or are planning on becoming pregnant during the study.
Study Procedures		
Spirometry procedures	This may cause difficulty breathing, changes in pulse rate and blood pressure, coughing, wheezing, chest tightness or fainting.	Subjects will be monitored during the procedure for these effects and spirometry will be discontinued should these occur.
ECG lead placement	This may cause skin irritation.	It may be necessary to have small patches (about a centimetre in diameter) of hair on the chest shaved to properly attach electrodes to the chest.
Blood sampling procedure (optional pharmacogenetic blood sample)	Giving blood may make subjects feel faint, or experience mild pain, bruising, irritation or redness at the site. In rare cases, they may get an infection	Subjects will be monitored during the blood draw for these effects and should call their study doctor if any of these effects do not resolve
Other		
Side effects of rescue albuterol/salbutamol. Adverse events seen in clinical studies to date are however consistent for the beta ₂ -adrenergic class of compounds	Class effects associated with short acting beta-agonists (SABAs)	Subjects should call their study doctor if they experience any of these symptoms

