5. SELECTION OF STUDY POPULATION AND WITHDRAWAL CRITERIA

Specific information regarding warnings, precautions, contraindications, adverse events, and other pertinent information on the GSK investigational product or other study treatment that may impact subject eligibility is provided in the IBs, [GlaxoSmithKline Document Number [RM2006/00835/09](#)], [GlaxoSmithKline Document Number [RM2009/00437/07](#)] and product labels.

Deviations from inclusion and exclusion criteria are not allowed because they can potentially jeopardize the scientific integrity of the study, regulatory acceptability or subject safety. Therefore, adherence to the criteria as specified in the protocol is essential.

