5.5. Withdrawal/Stopping Criteria

5.5.1. Withdrawal from the Study

Subjects may be withdrawn from the study at any time by the Investigator if it is considered to be detrimental for them to continue in the study. Reasons for withdrawal from study treatment can include: an AE, clinically significant abnormality, lack of efficacy, sponsor terminated study, pregnancy, or for any other reason.

If a subject withdraws from the study, he/she may request destruction of any samples taken, and the investigator must document this in the site study records.

A reason for the withdrawal from the study must be captured in the electronic case report form (eCRF).

Stopping Criteria

A subject must be withdrawn from the study, in consultation with the medical monitor and principal investigator, if any of the following stopping criteria are met:

- **Liver Chemistry:** Meets any of the Liver chemistry stopping criteria (See Section [5.5.3](#))
Note: clinical laboratory assessments are not required for this study. However, laboratory samples may be taken for liver event analysis, if clinically indicated by the study investigator.
- **Pregnancy:** Positive pregnancy test (see [Appendix 7](#))

- **Unstable or life threatening cardiac events:** myocardial infarction, hospitalization for unstable angina, stroke, and other cardiovascular events considered life- or intensively health-threatening by the study physician.
- **COPD Exacerbations:** Subjects with two moderate or one severe COPD exacerbation during the study.
- **Withdrawal from study treatment** requires withdrawal from the study.
- **Non-Compliance with Study treatment:** Subjects' compliance with study treatment will be assessed at each study visit. Subjects who are non-compliant should be re-educated on the requirement for treatment compliance. Every effort will be made to keep subjects in the study and to re-educate those subjects who continue to be non-compliant. Subjects who continue to be non-compliant after multiple visit assessments may be permanently discontinued **after consultation with the GSK clinical team.**
- **Non-Compliance with eDiary:** Subjects must be compliant in completing their eDiary between each pair of on-treatment visits. Subjects who are non-compliant should be re-educated on the requirement for daily diary entry compliance. Subjects who continue to be non-compliant after multiple visit assessments may be permanently discontinued **after consultation with the GSK clinical team.**

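### Section 4.6.1 gives different responses to paradoxical bronchospasm for UMEC/VI and UMEC; a blinded site cannot tell which applies, and no text makes the stop independent of arm

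*Protocol*

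**What the plan says.** Protocol Section 4.6.1 sets out risks and mitigation by product.

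- **UMEC/VI row.** "If paradoxical bronchospasm occurs following dosing with UMEC/VI, this treatment should be discontinued immediately and alternative therapy should be instituted".
- **UMEC row.** Rescue albuterol/salbutamol is supplied. Then: "The investigators will be instructed to assess subject's condition to determine their eligibility to" (the row breaks across a page here) "continue in the study and the need for alternative therapy".
- **Salmeterol.** The table has no block for it. Section 4.6 points elsewhere: "Summary safety data can also be found in the information sheet for salmeterol". Section 5 refers to the brochures and product labels for "Specific information regarding warnings, precautions, contraindications, adverse events, and other pertinent information on the GSK investigational product or other study treatment".

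Section 5.5.1 has a general clause and a mandatory list. The general clause reads "Subjects may be withdrawn from the study at any time by the Investigator if it is considered to be detrimental" and continues: "Reasons for withdrawal from study treatment can include: an AE, clinically significant abnormality, lack of efficacy". The mandatory part requires withdrawal "if any of the following stopping criteria are met". It lists liver chemistry, pregnancy, unstable or life-threatening cardiac events, COPD exacerbations (two moderate or one severe), withdrawal from study treatment, and non-compliance with treatment or with the eDiary. Paradoxical bronchospasm is not on it.

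Section 6.5 makes the trial double-blind and double-dummy. It permits the investigator to unblind in an emergency or a serious medical condition, and requires withdrawal of any subject whom the investigator or treating physician has unblinded.

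**The concern.** The response to one acute event depends on a fact that the site does not have. The UMEC/VI row rules out further dosing; the UMEC row allows a decision to continue. A site that follows the UMEC row in good faith could keep dosing a subject who is in fact on UMEC/VI, for whom the protocol wants treatment stopped. Nothing says which row prevails when the arm is unknown, and a salmeterol subject has no stated response in the table at all. What is at stake is the safety of the individual subject and consistent handling across sites, not the efficacy conclusion.

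**Working it through.** The protocol states no figure on this point, so there is nothing to reproduce. The check sets the sections side by side.

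1. **Is it the same event?** Yes. Both rows call it paradoxical bronchospasm, both say that it may threaten life, and both attribute it to inhaled therapy in general. The table gives no reason for a different response by product.

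2. **Are the responses different?** Yes. One is an immediate stop with alternative therapy. The other is an assessment in which continuing is a permitted outcome.

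3. **Can a blinded site tell which row applies?** No. Under Section 6.1 and the double-dummy design every subject uses both ELLIPTA and DISKUS, so neither the regimen nor the device in use identifies the arm.

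4. **Does unblinding resolve it?**
   - If the subject turns out to be on UMEC/VI, Section 6.5 leads to withdrawal, which agrees with the UMEC/VI row.
   - If the subject turns out to be on UMEC, Section 6.5 also leads to withdrawal, so the option to continue is gone as soon as the arm is known.
   - The UMEC option is therefore usable only by a site that has not unblinded, and such a site has not excluded UMEC/VI.

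5. **Is there one action that satisfies both rows while blinded?** Yes. Stopping treatment does what the UMEC/VI row asks and is also a permissible result of the UMEC assessment.

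6. **Does any text require that action whatever the arm?** No.
   - The UMEC/VI row is tied to dosing with UMEC/VI.
   - The general clause of 5.5.1 is permissive.
   - The mandatory list in 5.5.1 omits the event, although its other criteria are worded without reference to arm.

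The two rows are thus compatible if a site chooses to stop everyone. The protocol does not tell it to do so, and one row expressly leaves the other choice open.

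**The case against.** The strongest reply is that a safe default is already in the text. A site that does not know the arm can stop every subject and comply with the whole table. The UMEC row does not direct continued dosing; it asks for an assessment. Because both rows present the event as common to inhaled medicines, a careful reader would lean towards stopping. Section 5.5.1 lets the investigator withdraw a subject at any time, with an adverse event as a named reason. Section 6.5 gives direct access to the treatment code without prior contact with the sponsor. Section 7.4.1.3 has adverse events of special interest, defined by reference to 4.6.1, followed until they resolve or stabilise. The 5.5.1 list is also not the only source of withdrawal rules, since the unblinding rule sits in 6.5. Finally, the brochures, labels and site instructions are not at hand and may say more.

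Most of this stands, and it is why the point is minor. It does not remove the conflict. Discretion to stop is not an instruction to stop, the follow-up acts after the event, and the unseen sources would not change the wording of the two rows.

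A lighter remedy, a cross-reference between the two rows, would reconcile them but would leave salmeterol without a stated response.

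Three stronger readings are tempting and are not supported:

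- A reader might infer that a blinded site cannot act safely, or that the protocol makes it continue. Step 5 shows otherwise.
- A reader might infer that stopping waits for serious adverse event reporting or for the sponsor to unblind, so that another dose falls due first. No section makes the stop wait; the investigator can stop at once.
- A reader might turn the 1:1:1 allocation into a chance that a subject who continues is on UMEC/VI. That would need event rates by arm, and a decision to continue that is unrelated to arm. The protocol provides neither.

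**Conclusion.** The point holds as a minor conflict in safety wording. Section 4.6.1 prescribes a stop for one arm, leaves continuation open for another and is silent on the third, and no text makes the stop independent of arm. The UMEC option can be used only while UMEC/VI has not been excluded.

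Its size cannot be put in numbers: the protocol gives no rate of paradoxical bronchospasm and no indication of how often a site would continue treatment. It has no effect on the primary estimate. The conclusion rests on the protocol text alone and assumes that the brochures, labels and site instructions do not already impose a single stop for all arms, which cannot be checked here. It is a cheap improvement.

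**What to change.** Add one criterion to the mandatory list in Section 5.5.1: if the investigator judges that paradoxical bronchospasm followed study treatment in any arm, both the ELLIPTA and the DISKUS are stopped immediately, without needing to unblind; alternative therapy is started; and the subject is withdrawn through the existing Early Withdrawal Visit and safety follow-up contact. Have both paradoxical bronchospasm rows in Section 4.6.1 refer to that criterion, and state that it also covers salmeterol.

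Withdrawal is consistent with the existing rule in 5.5.1 that ending study treatment ends study participation. The cost is one bullet and two cross-references at the next amendment, with no new procedure or data collection. The downside is that UMEC and salmeterol subjects lose the option to continue after such an event, so a few more withdrawals are possible in those arms.
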